4.3 JUSTIFICATION FOR DOSE

4.3.1 PHASE 1B:

The Dose Escalation Phase 1b part will utilize a "3+3" design for escalation. The study plan includes the evaluation of 3 planned dose levels of cabozantinib administered orally. A minimum of 6 and a maximum of 18 subjects will be enrolled in each dose escalation cohort in Phase 1b, starting at 40 mg daily. The Sponsor reserves the right to adjust the planned cabozantinib dose levels based on emerging study data (Note: This will be considered as a protocol amendment) The planned cabozantinib dose levels to be studied in the Dose Escalation Phase 1b are presented in table 1. If the MTD has not been identified at the highest planned dose level, the Sponsor reserves the right to consider additional dose levels, and this would require a protocol amendment.

Table 1: Planned Dose Levels of Cabozantinib and Pembrolizumab

Dose Level	Cabozantinib	Pembrolizumab
-1	20 mg	200 mg
0 (starting dose)	40 mg	200 mg
1	60 mg	200 mg

Pembrolizumab will be administered at a standard recommended (drug label) dosing of 200 mg intravenously once every 3 weeks.

DLTs are defined in Section 4.3.2 Part 1 Dose Escalation: Dose-Limiting Toxicities (DLTs). The DLT rate across all subjects enrolled within a cohort in phase 1 must be <33% to allow escalation to the next dose level in that Arm. *The DLT observation period is 21 DAYS from date of first dose of cabozantinib.*

At the start of any new cohort, there will be a waiting period of at least 1 week after the first dose of the 3rd subject before enrollment of additional subjects into the same cohort. If a subject withdraws from the study prior to completion of the DLT assessment period for a reason other than a DLT, a replacement subject will be enrolled in that cohort.

Dose escalation in Part 1 to the next dose level can only occur after a minimum of 3 subjects have completed their DLT observation period for the current dose level, and the DLT rate does not exceed 33%.

Prior to escalation to a new dose level, the Safety Review Committee (SRC) will meet to review the safety data from the current cohort in order to determine if dose escalation is warranted.

The following rules govern dose escalation in Phase 1b:

- If none of the initial 3 subjects at a dose level experiences a DLT, escalation to the next dose level may occur. However, the Sponsor reserves the right to enroll up to 12 subjects in a cohort in order to obtain additional safety information.

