4.3.2 PHASE 1B: DOSE-LIMITING TOXICITIES (DLTS)

Standard safety monitoring will be employed for DLT assessment and dose-escalation decisions. All AEs will be considered in DLT assessment unless an event is clearly unrelated to trial treatment. DLTs for phase 1b are defined below and only include AEs that are considered possibly, probably, or definitely related to the cabozantinib plus Pembrolizumab regimen which occur *during the first 21 days of therapy*. All AEs, including DLTs, are to be reported and graded using NCI CTCAE, Version 4.03.

The following AEs will be considered DLTs **if deemed related to study therapy**:

- Hematologic

- o Asymptomatic Grade 4 neutropenia lasting for > 5 days.
- o Febrile neutropenia, defined as absolute neutrophil count (ANC) <1000/mm³ with a temperature of \geq 38.3 degrees C
- o Grade \geq 3 neutropenic infection
- o Grade \geq 3 thrombocytopenia with bleeding
- o Asymptomatic Grade 4 thrombocytopenia lasting for > 5 days.

- Non-hematologic:
 1. All non-hematologic Grade \geq 3 adverse events at least possibly related to study treatment of any duration must be DLTs with the following exceptions:
 - i. Transient (\leq 72 hours) abnormal laboratory value without associated clinically significant signs or symptoms
 - ii. Nausea, vomiting, or diarrhea adequately controlled with supportive care within 48 hours
 - iii. Alopecia
 - iv. Grade 3 fatigue in a patient with Grade 1 or Grade 2 fatigue at baseline
 - v. hypertension
 2. Any related \geq Grade 3 AE which is unexpected in severity and/or duration compared to the known safety profiles of cabozantinib and pembrolizumab when used as single agents, and that cannot be managed by dose modification (reductions or interruption) and adequate supportive care, requires permanent discontinuation of cabozantinib and/or pembrolizumab.
 3. Inability to take \geq 75% of the total planned cabozantinib dose for the DLT Evaluation Period because of a treatment-related AE leading to dose reductions and/or interruptions.

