- Interruption of cabozantinib treatment for AEs may occur at any time per investigator discretion. If treatment is interrupted due to AEs for more than 6 weeks, patient will be taken off study unless the investigator deems there to be previous or ongoing clinical benefit.
- Dose interruptions for reason(s) other than AEs (eg, surgical procedures) can be longer than 6 weeks but require Sponsor approval. The acceptable length of interruption will depend on agreement between investigator and the Sponsor.
- Dose interruptions may occur in 2 ways:
 - Within a cycle:** If dosing interruption and/or dose reduction occurs between Day 1 and Day 21 of a cycle (including protocol-specified windows), the cycle proceeds as planned.
 - Prior to the initiation of a new cycle:** If the investigator decides on day 1 of a new cycle that dose interruption should occur, that cycle may be delayed. When the investigator decides that dosing should resume, the day that the patient restarts drug will be day 1 of that new cycle. Re-escalation to any previous dose may be allowed at the discretion of the investigator no sooner than 2 weeks beyond resolution of AEs that led to the dose reduction. Dose re-escalation is not allowed for a previous dose reduction triggered by Grade 4 hematologic toxicities or by Grade 4 AEs affecting major organs (eg, central nervous system, cardiac, hepatic, renal).

Table 4: Dose Modifications of Cabozantinib for Treatment Related AEs

CTCAE v4.0	Recommended Guideline for Management
Grade 1 AEs	Supportive care as indicated. Continue cabozantinib at the current dose level if AE is manageable and tolerable.
Grade 2 AEs which are tolerable and are easily managed	Continue cabozantinib at the current dose level with supportive care.
Grade 2 AEs which are intolerable and cannot be adequately managed	At the discretion of the investigator, cabozantinib should be dose reduced or interrupted. Note: It is recommended that dose holds be as brief as possible.
Grade 3 AEs (except clinically non-relevant laboratory abnormalities)	Cabozantinib should be interrupted unless the toxicity can be easily managed with a dose reduction and optimal medical care. Note: It is recommended that dose holds be as brief as possible
Grade 4 AEs (except clinically non-relevant laboratory abnormalities)	Subjects should have cabozantinib interrupted immediately.

Discontinue cabozantinib unless the following criteria are met:

<

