6.6 CONCOMITANT THERAPY

All treatments that the investigator considers necessary for a subject's welfare may be administered at the discretion of the investigator in keeping with the community standards of medical care. All concomitant medication will be recorded on the case report form (CRF) including all prescription, over the counter (OTC), herbal supplements, and IV medications and fluids. If changes occur during the trial period, documentation of drug dosage, frequency, route, and date will also be included on the CRF.

Palliative and supportive care is permitted during the course of the trial for underlying medical conditions and management of symptoms. Surgery for tumor control or symptom management is not permitted during the study. Palliative radiotherapy is permitted to a single lesion if considered medically necessary by the treating physician as long as the lesion is NOT a RECIST 1.1 defined target lesion and is radiation is NOT administered for tumor control. Cabozantinib should be held during the course of palliative radiotherapy and

resumed 1 week after completion of palliative radiotherapy. The specifics of the radiation treatment, including the location, will be recorded. All concomitant medications received within 30 days before the first dose of trial treatment through 30 days post last dose or until new treatment is started, whichever occurs first should be recorded.

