6.6.5 POTENTIAL DRUG INTERACTIONS WITH CABOZANTINIB

Cytochrome P450: Data from a clinical drug interaction study (Study XL184-008) show that clinically relevant steady-state concentrations of cabozantinib appear to have no marked effect on the area under the plasma concentration-vs-time curve (AUC) of co-administered rosiglitazone, a CYP2C8 substrate. Therefore, cabozantinib is not anticipated to markedly inhibit CYP2C8 in the clinic, and by inference, is not anticipated to markedly inhibit other CYP450 isozymes that have lower [I]/Ki values compared to CYP2C8 (ie, CYP2C9, CYP2C19, CYP2D6, CYP1A2, and CYP3A4). In vitro data indicate that cabozantinib is unlikely to induce cytochrome P450 enzymes, except for possible induction of CYP1A1 at high cabozantinib concentrations (30 μ M).

Cabozantinib is a CYP3A4 substrate and a weak substrate for CYP2C9 (but not a CYP2D6, CYP2C8, CYP2C19, CYP2B6, or CYP1A2 substrate), based on data from in vitro studies. Results from a clinical pharmacology study, XL184-006, showed that concurrent administration of cabozantinib with the strong CYP3A4 inducer, rifampin, resulted in an approximately 77% reduction in cabozantinib exposure (AUC values) after a single dose of cabozantinib in healthy volunteers. Chronic co-administration of cabozantinib with strong inducers of the CYP3A4 family (eg, phenytoin, carbamazepine, rifampin, rifabutin, rifapentine, phenobarbital, and St. John's Wort) may significantly decrease cabozantinib concentrations. The chronic use of strong CYP3A4 inducers should be avoided. Other drugs that induce CYP3A4 should be used with caution because these drugs have the potential to decrease exposure (AUC) to cabozantinib. Selection of alternate concomitant medications with no or minimal CYP3A4 enzyme induction potential is recommended.

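### Phase 1b sets no minimum cabozantinib exposure for a DLT-free subject, so one who stays on study but misses 6 or more of 21 doses for a non-toxicity reason counts as tolerating the dose

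*Combined protocol and SAP*

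**What the plan says.** Section 4.3.1 sets the counting rules for Phase 1b.

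- Replacement: "If a subject withdraws from the study prior to completion of the DLT assessment period for a reason other than a DLT, a replacement" subject is enrolled. No other ground is given.
- Denominator: "The DLT rate across all subjects enrolled within a cohort in phase 1 must be <33% to allow escalation to the next dose level".
- Window: "The DLT observation period is 21 DAYS from date of first dose of cabozantinib". These are calendar days, not days on drug.
- Precondition: escalation "can only occur after a minimum of 3 subjects have completed their DLT observation period for the current dose level".

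Section 4.3.2 item 3 contains the only exposure threshold. Being unable to take at least 75% of the "total planned cabozantinib dose for the DLT Evaluation Period because of a treatment-related AE" is a DLT. A shortfall with any other cause is not mentioned.

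Elsewhere the protocol allows cabozantinib to be held without the subject leaving the study. Section 6.1.2.3 states: "Dose interruptions for reason(s) other than AEs (eg, surgical procedures) can be longer than 6 weeks but require Sponsor approval". Section 6.6 states: "Cabozantinib should be held during the course of palliative radiotherapy and" restarted one week after it ends. Section 6.2.1 describes holds of about 4 weeks before an unavoidable dental procedure and, where clinically possible, at least 28 days before scheduled surgery.

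Section 9.2 requires 6 to 18 *evaluable* patients in Phase 1 and does not define the word. Section 9.3 defines only a safety and an mITT population. Section 9.4.2 sets the RP2D as the highest level with at most 1 DLT in 6 patients.

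**The concern.** A 3+3 design reads the absence of a DLT as evidence that the dose was tolerated. That holds only if the subject took the dose. Item 3 of 4.3.2 shows that the authors regard intake below 75% as material, but the rule works in one direction: under-dosing from toxicity counts against the level, while the same under-dosing from another cause counts in its favour.

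Section 6.2.1 gives a 99-hour half-life and 2 to 3 weeks to steady state, so a hold inside a 21-day window can keep a subject from ever reaching full exposure while under observation.

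Each level rests on as few as 3 to 6 subjects, and the RP2D goes to every Phase 2 patient. A single uninformative subject therefore carries real weight, and the error favours passing the level.

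**Working it through.** **The plan's own figure.** With 3 to 6 subjects per level, the minimum is 2 levels × 3 = 6 and the maximum is 3 levels × 6 = 18. This matches 9.2. (Section 4.3.1 attaches the same 6 to 18 to each cohort, which should be reconciled with 9.2.)

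**When the 75% threshold bites.** 0.75 × 21 = 15.75 doses. Five missed doses leave 16/21 = 76.2%; six leave 15/21 = 71.4%. So, at an unchanged daily dose, six or more missed doses are a DLT if a treatment-related AE caused them. Otherwise they leave the subject DLT-free, in the denominator and not replaced.

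**Chance of passing a level.** Rule from 4.2.1: pass on 0 of 3, or on 1 of the first 3 followed by 0 of the next 3. Let p be the true DLT rate at full exposure, and a0 and a1 the probabilities of 0 and 1 DLT in the first three. Then P(pass) = a0 + a1 × (1−p)^3.

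- All three exposed: a0 = (1−p)^3; a1 = 3p(1−p)^2.
- One at zero risk: a0 = (1−p)^2; a1 = 2p(1−p).
- One at half risk: a0 = (1−p)^2(1−p/2); a1 = 2p(1−p)(1−p/2) + (1−p)^2(p/2).

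Worked at p = 0.4, where (1−p)^3 = 0.216:

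- All exposed: 0.216 + 0.432 × 0.216 = 0.309.
- Zero risk: 0.360 + 0.480 × 0.216 = 0.464.
- Half risk: 0.288 + 0.456 × 0.216 = 0.386.

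| True DLT rate | All exposed | One at half risk | One at zero risk |
|---|---|---|---|
| 1/6 (3+3 target rate, 4.2.1) | 78.0% | 81.7% | 85.5% |
| 33% | 43.4% | 50.8% | 58.2% |
| 40% | 30.9% | 38.6% | 46.4% |
| 50% | 17.2% | 24.2% | 31.2% |

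The rates other than 1/6, and the zero and half risks, are assumptions. Zero risk is a worst case.

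**Without conditioning on the event.** The documents give no frequency for under-exposure. If each subject independently had a 5% chance of no exposure (an assumption), the effective rate would be 0.95p. At p = 0.4 that is 0.38, and P(pass) = 0.62^3 + 3 × 0.38 × 0.62^2 × 0.62^3 = 34.3%, against 30.9%. At p = 1/6 it is 79.7%, against 78.0%.

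**Strong CYP3A4 inducer.** Section 6.6.5 reports that rifampin "resulted in an approximately 77% reduction in cabozantinib exposure (AUC values) after a single dose of cabozantinib" in healthy volunteers. If that applied in full (an assumption), 40 mg would act as 40 × 0.23 = 9.2 mg and 60 mg as 60 × 0.23 = 13.8 mg, both below the lowest planned level of 20 mg.

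**The case against.** The strongest reply is that the routes to under-exposure are mostly closed.

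- Exclusion 22 bars present use or expected need of strong CYP3A4 inducers or inhibitors, with washouts before registration, and 6.6.4 says they should be avoided on study.
- Exclusion 7 bars patients expected to need other antineoplastic therapy, local or systemic.
- Section 6.6.4 advises against palliative radiation before RECIST progression is established, and the first on-study scan is at week 12.
- Section 5.2 requires recent surgery to be past and healed, and 6.6 bars surgery for tumour control or symptom management.
- Section 7.2 lists noncompliance with the schedule as a reason for withdrawal from treatment.

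In addition, escalation only *may* occur, a committee reviews each cohort first, up to 12 subjects may be enrolled per cohort, and pills are counted every cycle.

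Much of this stands: the event should be uncommon and escalation is not automatic. It does not close the gap. The committee has no evaluability criterion. Withdrawal from treatment is not clearly the withdrawal from the study that 4.3.1 requires, and a permitted hold is not noncompliance. The entry criteria do not say how an on-study shortfall is counted.

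Zero risk also overstates a partly dosed case: pembrolizumab is due on Day 1, and cabozantinib already taken clears slowly.

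A reader might also want strong inhibitors treated like inducers. The documents do not support that. Section 6.6.5 reports 38% higher exposure with ketoconazole, which makes a DLT more likely. Replacing inhibitor-exposed subjects only when they have no DLT would discard evidence of tolerability at higher exposure and inflate the DLT rate.

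**Conclusion.** The gap is in the stated rules. Withdrawal from the study is the only ground for replacement, the rate runs over all enrolled subjects, and under-dosing counts only when toxicity caused it. *Evaluable* in 9.2 is undefined and is not reconciled with the all-enrolled denominator in 4.3.1.

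Given one such subject among the first three, the chance of passing a level rises by about 4 to 8 percentage points at a true DLT rate of 1/6, 8 to 15 at 40%, and 7 to 14 at 50%. The lower figure assumes half risk for that subject and the upper assumes none. These are conditional illustrations, not estimates of the trial's overall error; with the assumed 5% frequency the shift is 3.4 points at 40% and 1.7 points at 1/6.

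A reader might infer that escalation follows automatically or that the RP2D is too high. The documents support neither: the committee decides on escalation, and no frequency or Phase 1b data are given. The point merits correction because the rule is asymmetric and cheap to repair.

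**What to change.** In 4.3.1, 9.2 and 9.4.2, define a DLT-evaluable subject as one who has a DLT, or who completes Day 21 having received the first pembrolizumab dose and at least 75% of planned cabozantinib. Replace any other subject. Base every escalation and RP2D count on DLT-evaluable subjects, in place of the all-enrolled denominator. Keep all treated subjects in the safety tables.

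A subject without a DLT who took a strong CYP3A4 inducer on Days 1 to 21 may also be classed as non-evaluable. Do not add a matching clause for inhibitors.

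Sections 6.6 and 6.6.4 conflict on palliative radiotherapy during treatment and must be reconciled.

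The cost is a few sentences, an occasional replacement subject and a short delay. Pill counts and concomitant medications are already recorded, and no dose or patient management changes. If escalation is already complete, apply the definition to the existing records and report the result as a check on the RP2D.

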4.3.2 PHASE 1B: DOSE-LIMITING TOXICITIES (DLTS)

Standard safety monitoring will be employed for DLT assessment and dose-escalation decisions. All AEs will be considered in DLT assessment unless an event is clearly unrelated to trial treatment. DLTs for phase 1b are defined below and only include AEs that are considered possibly, probably, or definitely related to the cabozantinib plus Pembrolizumab regimen which occur *during the first 21 days of therapy*. All AEs, including DLTs, are to be reported and graded using NCI CTCAE, Version 4.03.

The following AEs will be considered DLTs **if deemed related to study therapy**:

- Hematologic

- o Asymptomatic Grade 4 neutropenia lasting for > 5 days.
- o Febrile neutropenia, defined as absolute neutrophil count (ANC) <1000/mm³ with a temperature of \geq 38.3 degrees C
- o Grade \geq 3 neutropenic infection
- o Grade \geq 3 thrombocytopenia with bleeding
- o Asymptomatic Grade 4 thrombocytopenia lasting for > 5 days.

- Non-hematologic:
 1. All non-hematologic Grade \geq 3 adverse events at least possibly related to study treatment of any duration must be DLTs with the following exceptions:
 - i. Transient (\leq 72 hours) abnormal laboratory value without associated clinically significant signs or symptoms
 - ii. Nausea, vomiting, or diarrhea adequately controlled with supportive care within 48 hours
 - iii. Alopecia
 - iv. Grade 3 fatigue in a patient with Grade 1 or Grade 2 fatigue at baseline
 - v. hypertension
 2. Any related \geq Grade 3 AE which is unexpected in severity and/or duration compared to the known safety profiles of cabozantinib and pembrolizumab when used as single agents, and that cannot be managed by dose modification (reductions or interruption) and adequate supportive care, requires permanent discontinuation of cabozantinib and/or pembrolizumab.
 3. Inability to take \geq 75% of the total planned cabozantinib dose for the DLT Evaluation Period because of a treatment-related AE leading to dose reductions and/or interruptions.

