6.2.1 CABOZANTINIB

The side effect profile of cabozantinib includes GI symptoms (such as nausea, vomiting, and diarrhea), fatigue/asthenia, anorexia, weight loss, skin rash including PPE syndrome, mucosal inflammation/stomatitis, and hypertension. Subjects may also experience medically important but less frequent adverse events including arterial and venous thrombotic events such as deep vein thrombosis (DVT), pulmonary embolism (PE), transient ischemic attack, and myocardial infarction; severe hemorrhagic events, proteinuria, wound healing complications, GI perforation, intraabdominal and pelvic abscess, GI and non-GI fistulae formation, osteonecrosis, and reversible posterior leukoencephalopathy syndrome (RPLS).

Common laboratory abnormalities reported as AEs include ALT increased, AST increased, TSH increased, hypokalemia, hypomagnesemia, hypophosphatemia, hypocalcemia, lipase increased, and thrombocytopenia.

Please refer to the Investigator's Brochure for additional details.

As with all investigational products, unknown AEs may occur. Subjects should be monitored closely for all AEs. The predicted effective plasma half-life of cabozantinib is 99 hours.

Thus, when initiating therapy with cabozantinib, it will take most subjects 2-3 weeks to reach steady state. If AEs attributable to cabozantinib occur within the initial 3-week period of dosing, early intervention with dose modifications may be justified for AEs that, if worsened, could potentially be dangerous or debilitating, since without a dose adjustment, systemic exposure of cabozantinib might be expected to increase after the onset of the AE.

Cabozantinib should be discontinued for the following adverse events: visceral perforation or fistula formation, severe hemorrhage, serious arterial thromboembolic events (e.g MI, cerebral infarction), nephrotic syndrome, malignant hypertension, hypertensive crisis, persistent uncontrolled hypertension despite optimal medical management, osteonecrosis of the jaw (ONJ), and RPLS.

Management of gastrointestinal disorders, hepatobiliary disorders, hematological disorders, fatigue, anorexia, weight loss, skin disorders, hypertension, thromboembolic events,

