Step 4) If BP still not controlled, consider either 1 dose reduction of cabozantinib or stopping cabozantinib.

NOTE: Stopping or reducing the dose of cabozantinib is expected to cause a decrease in BP. The treating physician should monitor the patient for hypotension and adjust the number and dose of antihypertensive medication(s) accordingly.

Grade 3 Hypertension (Systolic ≥ 160 Diastolic ≥ 100), hold cabozantinib until systolic BP ≤ 159 and diastolic BP ≤ 99 .

Antihypertensive Therapy: BP management is identical to that for grade 2 (see steps 1-4 above) with 2 major exceptions:

- 1) If systolic BP > 180 or diastolic BP > 110 and the patient is symptomatic:** consider inpatient hospitalization and management as clinically indicated.
- 2) If systolic BP > 180 or diastolic BP > 110 and the patient is asymptomatic,** 2 new antihypertensives must be given together in step 1 (and dose escalated appropriately as in step 1).

NOTE: Stopping or reducing the dose of cabozantinib is expected to cause a decrease in BP. The treating physician should monitor the patient for hypotension and adjust the number and dose of antihypertensive medication(s) accordingly.

Dose Modification: HOLD cabozantinib until systolic BP < 159 and diastolic BP < 99 . In most circumstances, if BP cannot be controlled after an optimal trial of antihypertensive medications, consider either 1 dose reduction of cabozantinib or stopping cabozantinib.

HOWEVER, if the patient requires hospitalization for management of symptomatic systolic BP > 180 or diastolic BP > 110 , permanently discontinue cabozantinib or if BP is controlled, re-start cabozantinib at one lower dose level after consultation with the Study Chair.

Grade 4 Hypertension (life-threatening consequences of hypertension)

Antihypertensive Therapy: Optimal management in inpatient setting. Recommend ICU support and IV medication. STOP cabozantinib and notify hospital staff that stopping cabozantinib may result in a decrease in BP.

Dose Modification: Permanently discontinue cabozantinib or if BP is controlled, re-start cabozantinib at 1 lower dose level after consultation with the Study Chair.

THROMBOEMBOLIC EVENTS

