9.4.2 ANALYSIS OF THE PRIMARY EFFICACY ENDPOINT(S)

Phase I:

There are no primary efficacy endpoints for Phase I. The recommended Phase II dose is defined as the highest dose level for which at most 1 out of 6 patients experience a DLT.

Phase II:

The primary efficacy endpoint is ORR. ORR is defined as the proportion of patients with RECIST disease response (CR, PR). All patients that do not meet the criteria for an objective response by the analysis cutoff date will be considered non-responders.

Phase II is utilizing an optimal Simon's two-stage design. As such, 14 patients will be enrolled in the first stage. If 5 or fewer patients respond (CR or PR), the study will be terminated due to futility. Otherwise, an additional 30 patients will be enrolled in the second stage. As per the decision rules of the design, the null hypothesis will be rejected if at least 21 patients respond (CR or PR) out of the 44 total patients. The ORR and 95% exact confidence interval will be reported.

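### DLT exception v exempts hypertension of any grade from item 1, and items 2 and 3 only partly bring back Grade 4 or treatment-ending events

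*Combined protocol and SAP*

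**What the plan says.** All references are to the combined protocol and SAP.

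- **4.3.2, item 1.** Related non-hematologic events of Grade 3 or worse are DLTs, with five exceptions. Exception i (laboratory values) is limited to 72 hours without clinically significant signs or symptoms. Exception ii (nausea, vomiting, diarrhea) requires control within 48 hours. Exception iv is limited by grade and baseline status: "Grade 3 fatigue in a patient with Grade 1 or Grade 2 fatigue at baseline". Exception iii (alopecia) has no limit. Exception v is, in full, "v. hypertension".
- **4.3.2, item 2.** A related Grade ≥3 event counts if it is unexpected against the single-agent profiles "and that cannot be managed by dose modification (reductions or interruption) and adequate supportive care".
- **4.3.2, item 3.** A patient counts who cannot take at least 75% "of the total planned cabozantinib dose for the DLT Evaluation Period because of a treatment-related AE".
- **6.2.1, general text.** Events for which cabozantinib should be discontinued include "malignant hypertension, hypertensive crisis, persistent uncontrolled hypertension despite optimal medical management".
- **6.2.1, Hypertension.** The highest tier is headed "Grade 4 Hypertension (life-threatening consequences of hypertension". Its dose instruction is: "Permanently discontinue cabozantinib or if BP is controlled, re-start cabozantinib at 1 lower dose level after consultation with the Study Chair".
- **9.4.2.** The recommended Phase 2 dose is the "highest dose level for which at most 1 out of 6 patients experience a DLT".

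**The concern.** Three of the other four exceptions stop at some limit of duration, control or grade. The fourth, alopecia, has none, but nothing in the plan makes alopecia a reason to stop cabozantinib. Hypertension is different: section 6.2.1 treats its worst forms as life-threatening and as grounds for stopping the drug, yet item 1 passes over them at every grade.

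The DLT count decides the dose. One uncounted patient can turn 1 of 3 (expand the cohort) into 0 of 3 (escalate), or 2 of 6 (stop) into 1 of 6 (pass). The chosen dose then goes to as many as 44 Phase 2 patients. The question is how much of this gap items 2 and 3 close.

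**Working it through.** The plan gives no figure for this gap, so there is none to reproduce.

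**Inputs.** The window is 21 days with one dose a day (4.3.1, 6.1.2.1). The dose levels are 20, 40 and 60 mg (Table 1). The item 3 limit is 75%. The following are assumptions: onset is uniform over the 21 days, a permanent stop counts as an interruption under item 3, and the length of any hold is as shown below.

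**Item 2.** The wording of its last clause, on permanent discontinuation, is unclear, but on any reading the event must be both unexpected and unmanageable. Failing either test is enough to escape.
- Severe hypertension can fairly be called expected. Pooled Grade 3/4 rates on cabozantinib are 28% (randomized Phase 2 in renal cell carcinoma, 2.2.2.2), 15% (Phase 3 in renal cell carcinoma, 2.2.2.3) and 10% (melanoma trial at 100 mg, 2.3.2.1).
- A Grade 4 event restarted one level lower, as 6.2.1 permits, has been managed by dose modification.

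**Item 3, permanent stop.** The limit is 0.75 × 21 = 15.75 doses.
- 15/21 = 71.4%: a DLT.
- 16/21 = 76.2%: not a DLT.
- If the event comes after that day's dose, stops after doses 16 to 21 escape: 6/21 = 29%.
- If it comes before that day's dose, stops on days 17 to 21 escape: 5/21 = 24%.
- Item 3 catches the other 71–76%.

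**Item 3, hold and restart one level lower.** With d full doses before the event,

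dose taken = d × full dose + (21 − d − hold) × lower dose.

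The limits are 0.75 × 1260 = 945 mg from 60 mg and 0.75 × 840 = 630 mg from 40 mg. The table counts the event as coming after that day's dose.

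| Hold (days) | 60→40 mg: smallest escaping d | Share | 40→20 mg: smallest escaping d | Share |
|---|---|---|---|---|
| 2 | 10 (10×60 + 9×40 = 960) | 12/21 = 57% | 13 (13×40 + 6×20 = 640) | 9/21 = 43% |
| 3 | 12 (12×60 + 6×40 = 960) | 10/21 = 48% | 14 (14×40 + 4×20 = 640) | 8/21 = 38% |
| 4 | 14 (14×60 + 3×40 = 960) | 8/21 = 38% | 15 (15×40 + 2×20 = 640) | 7/21 = 33% |
| 5 or more | 16 (16×60 = 960) | 6/21 = 29% | 16 (16×40 = 640) | 6/21 = 29% |

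If the event comes before that day's dose, each share falls by 1/21. A long hold is plausible after a life-threatening event, so the bottom row is the more cautious guide.

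These shares concern item 3 alone. Events that item 2 catches must be removed, as must those with a separately coded related Grade ≥3 consequence (a myocardial infarction, for example), which is a DLT under item 1. The documents do not say how many there would be.

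**Effect on escalation, illustration only.** Under 3+3 with per-patient DLT probability p, the chance of escalating is (1−p)³ + 3p(1−p)²(1−p)³. Assume a 10% rate of other DLTs and an independent rate h of Grade 4 or treatment-ending hypertension. Now, with item 3 catching 15/21 of these, p = 1 − 0.9 × (1 − h × 15/21). After the fix, p = 1 − 0.9 × (1 − h).

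| Assumed h | Now | After fix | Difference (points) |
|---|---|---|---|
| 2% | 88.4% | 87.5% | 0.9 |
| 5% | 84.9% | 82.4% | 2.5 |
| 10% | 78.5% | 73.0% | 5.5 |

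An h of 10% is extreme: it equals the melanoma trial's pooled Grade 3/4 rate over the whole study at 100 mg.

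**The case against.** The best defense is the design rationale in 4.2.1. Escalation is meant to respond to toxicity that neither agent shows alone, or that exceeds what existing data predict. Hypertension is a known cabozantinib effect, so exempting it in item 1 and leaving item 2 to catch unexpected severity follows that logic. This stands for manageable Grade 3 hypertension. It does not explain an exemption that reaches life-threatening events, and item 1 does not exempt expected toxicities in general.

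The escaping set is also narrow. The event must be severe, must come late or be followed by a short hold, must fail item 2, and must have no separately coded Grade ≥3 consequence. To change a decision, it must also fall where one more DLT matters. Sustained blood pressure at or above 150/90 mm Hg despite optimal treatment is already an exclusion (5.2). All of this stands and limits the size of the problem.

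Finally, the event would be seen. The Safety Review Committee reviews cohort data before escalation (4.3.1), and serious adverse events are reported within 24 hours (11.0). The committee could decline to escalate. But no rule makes the event count, and the definition in 9.4.2 uses only the DLT count. The committee's review is tied to escalation, so it helps less at 60 mg, the maximum allowed level.

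**Conclusion.** The gap is real but partial. A permanent stop after 16 or more doses, or a late Grade 4 event managed by a hold and one reduction, can be scored as no DLT when it is judged expected or manageable and no separate consequence is coded. Under uniform timing, about 24–29% of permanent stops escape item 3. The effect on escalation is probably small and cannot be fixed from the documents, which give no rate for Grade 4 or treatment-ending hypertension.

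Three stronger readings are tempting and are not supported:
- **Severe hypertension can never be a DLT.** Items 2 and 3 still apply, and item 3 catches most permanent stops under the same timing assumption.
- **At least 29% of such events escape.** The figure rests on uniform onset and on the event following that day's dose, and item 2 and separately coded events lower it. Timing could also push it up: 6.2.1 says steady state takes most subjects 2–3 weeks, so events may cluster late. That is an inference, not trial data.
- **The 10–28% rates measure the gap.** They pool Grades 3 and 4 over whole studies and are not restricted to the first 21 days.

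The change is worth making because it is cheap and concerns safety, not because a large effect has been shown.

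**What to change.** In 4.3.2, change exception v to *Grade 3 hypertension* and add:

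> Grade 4 hypertension, or any hypertension with onset in the 21-day window that leads to permanent discontinuation of cabozantinib (including hypertensive crisis or malignant hypertension), is a DLT whatever share of the planned dose was taken.

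The clause should turn on onset, not on the date of the stop. The stepwise antihypertensive treatment in 6.2.1 can push the decision to stop past day 21. The sponsor should state how long after day 21 such a stop still counts. Any further condition on Grade 3 events, such as symptoms or time to control, can be left to the sponsor.

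The cost is one clause and a routine amendment, with review by the drug supplier and the IRB and no new visits or data. Slightly more events may count as DLTs, and a cohort decision may have to wait for a stop decision just after day 21. The documents do not say whether Phase 1b is complete. If it is, the same clause can be used to check whether any recorded hypertensive event would have changed a cohort's count.
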